Patients on peritoneal dialysis have frequent complications requiring hospitalization. Overhydration (OH), a qualitative description of fluid status, with excess fluid in the extracellular space [9], is one of the most common complications in PD patients. Clinical manifestations of OH include peripheral edema, congestive heart failure, pleural effusions, and hypertension [9]. It is estimated that 50-60% of PD patients are overhydrated, with severe OH producing clinical symptoms in 25% [10,11]. OH is associated with increased morbidity and mortality due to infections including peritonitis [12], and major adverse cardiovascular events such as myocardial infarction, pulmonary edema, stroke, and hypertensive crisis [9]. OH alone, independent of coexisting cardiovascular pathologies, is a risk for increased morbidity and mortality [13]. In 2016, at Srinagarind Hospital, at Khon Kaen University (KKU), Thailand, nearly half of the PD patients were hospitalized at least once, and some were hospitalized 2-4 times. Thirty-nine of the 91 patients (43%) were hospitalized a total of 77 times (some had 2-4 admissions). Sixty-five percent (50/77) of the hospitalizations were OH related (Table 1). The 5-year survival rate for PD patients is 48% [14]. Sixty-five percent of the PD admissions were for OH and related complications, with an average cost of \$3,000 USD/admission [14]. Extrapolating this data to a national level, the estimated cost for OH-related admissions in PD patients in Thailand is \$37,500,000 USD/year.

CKD and mobile health technology

Early treatment of overhydration can decrease complications and hospitalizations, improve quality of life, and decrease costs for PD patients. OH can be managed with treatments such as diuretics and anti-hypertensive medications, adjustments in dialysis prescriptions, and sodium/fluid restrictions [9,15]. Early detection of OH is possible by monitoring patients' hydration metrics: weight, blood pressure (BP), and ultrafiltration volume (difference between fluid input and output in dialysis). Currently, the critical gap lies in obtaining these hydration metrics in a timely and actionable format. A few studies have shown that smartphone and tele-monitoring programs are feasible and acceptable for patients with CKD [16-19]. Remote monitoring systems for PD patients

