the same hydration metrics - blood pressure (BP), weight, and ultrafiltrate volumes - using home monitoring equipment (BP cuff, body weight scale, and hanging scale). The no-app group will manually enter the information into their “PD logbook”- the handwritten paper booklet which is usual care. In contrast, the app group will automatically collect and enter the same information into the CKD-PD app using NFC technology on their smart phone. It will be displayed in the CKD-PD app for the patient and uploaded to the CKDNET database in the Thai Care Cloud; it then can be viewed on the CKD-PD web application by the PD clinic staff. Patients will monitor their hydration status on a graphical display on their smartphone. PD clinic staff will be notified daily about “action required” alerts on the web application. For example, systolic BP greater than 140 mmHg, diastolic BP greater than 90 mmHg, weight gain greater than 3% based on dry weight, or ultrafiltrate volume < 500 milliliters will trigger a response from the PD clinic. Nephrologists will make clinical interventions to treat OH according to standard practice in Thailand, which include BP and diuretic medication adjustments, change in diet or fluid intake, dialysis prescription adjustments or referral for urgent clinical evaluation. Clinical interventions can occur at unscheduled patient contact (e.g. patient call) or scheduled patient contact (routine clinic visit) Our primary outcome measure will be the incidence of clinical interventions for OH, both routine and urgent, in 1 year from enrollment. Secondary outcome measures include OH related complications, hospitalizations and deaths, and will be collected from PD clinic and hospital records, and the CKDNET database.

Setting and study population: The study will be conducted at the PD clinics at Srinagarind Hospital (N=100) the academic referral hospital affiliated with Khon Kaen University, Khon Kaen Hospital (N=50) the government referral hospital for Khon Kaen province, and Chaiyaphum Hospital (N=50), the government referral hospital for the neighboring Chaiyaphum province in northeast Thailand. We will recruit 200 patients with end-stage renal disease on PD from KKH to achieve a total sample size of 160.

Inclusion criteria are

- patients with CKD from any cause on home based peritoneal dialysis
- age ≥ 18
- access to a smartphone capable of running the CKD-PD app
- ability of the patient or surrogate to demonstrate successful use of the CKD-PD app

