Inclusion of children: We will enroll patients 18 years of age or older. The prevalence of PD in patients in Thailand under 18 years of age is <1% [8], therefore making it difficult to include this age group in our study. In addition, the etiologies of chronic kidney disease and co-morbidities are different in children and PD is used less frequently in children compared to hemodialysis.

Collaborating sites: None

Statistical Design and Power: We determined our sample size by using the difference in incidence rates between two Poisson means with 25% precision. Data collected from Srinagarind Hospital indicate the intervention rate for OH, based on current practice of patients contacting the PD clinic staff with symptoms or concerns of OH outside of scheduled appointments, to be 4 times/week in 91 patients or a mean intervention rate of 2.3 times/patient-year. Assuming a two-fold increase in the mean event rate for patients using the CKD-PD app or

4.6 times/patient-year in the CKD-PD app group, the desired sample size is 80 patients for each group, using a two-sided, large-samples z-test of the Poisson event-rate difference at a significance level of 0.05. Allowing for a 10% dropout rate, we will recruit a total of 200 patients (100 in each group). Our assumption that use of CKD-PD app will result in a twofold increase in the incidence of clinical interventions is based on our preliminary experience with the 42 patients currently using the CKD-PD app. In those 42 patients, especially those with unstable fluid and blood pressure control, the app frequently identifies outlier measurements resulting in intervention opportunities which are not possible in the no-app control group.

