Baseline variables of the CKD-PD app and no-app groups will be described by summary statistics. Percent distribution will be presented for all categorical variables. Mean with its standard deviation and median (Minimum: Maximum) will be presented for continuous variables. The primary outcome will be assessed by comparing the difference between the CKD-PD app group (intervention) and the no-app group (control), in incident rate (or Poisson count) of intervention for OH. A linear mixed model with an identity link and a Poisson distribution will be performed. By this modeling, the incidence rate difference and its 95% confidence interval will be estimated to answer the primary research question. Estimations will be adjusted for effects of important covariates that are imbalanced at baseline. Effect size will be calculated for secondary outcomes. All analyses will be performed using STATA version 14 (StataCorp, College Station, TX), using a significance level of 0.05. All statistical tests will be two-sided.

Randomization

Participants (Srinagarind N=100, Khon Kaen N=50, Chaiyaphum N=50) will be randomized into two equal groups at each site, one using the CKD-PD app (app group, N=50/25/25), and one receiving usual management (no-app group, N=50/25/25), using 4-block computer randomization in STATA. They will be assigned a PD clinic visit day based on their randomization allocation to reduce contamination or cross talk between the 2 study groups.

Delivery of intervention

Definition of study intervention:

Our study intervention is defined as the CKD-PD app, home hydration metric measurement equipment, and the monitoring of the uploaded hydration metrics to the CKDNET database.

Collection of hydration metrics: After enrollment, participants in both groups will undergo training on how to collect daily hydration metrics: body weight, blood pressure, and dialysate inflow and outflow volumes for each cycle. The app group will receive training on how to enter hydration metrics using NFC on the CKD-PD app, in

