Monitoring CKD-PD smartphone and web applications: We will set 3 categories to be used by PD clinic staff when monitoring hydration metrics on the CKD - PD web application: normal, monitor, and action required. Based on criteria specified by KKU nephrologists, deviations in weight of >3% from baseline dry weight, BP>140/90, and ultrafiltration volume of <500 ml will be used as baseline parameters for triggering an outlier alert for action required, indicating that the patient's hydration metrics need to be reviewed. We will also set critical values for hydration metrics, which require patient to go directly to the emergency department. We expect that some patients will require different parameters for triggering an outlier alert. In order to address this issue, a study nephrologist will provide normal and action required values for weight, blood pressure, and ultrafiltration volumes for each patient, at the time of enrollment after reviewing previous values from their PD logbook. During the study, the patient's nephrologist will have the option to modify the notification parameters. Hydration metric values between normal and action required will be categorized as monitor status.

PD clinic staff nurses will receive a list of patients with action required alerts once a day. They will review the hydration metrics and contact the patient(s), ask about symptoms, and have the nephrologist review the data and case to determine need for clinical intervention.

PD patients will also have the ability to self-monitor using the visual display of hydration metrics on the CKD-PD app. Planned features to simplify patients understanding of their fluid status include color coded zones corresponding to the normal (green), monitor (yellow), and action required (red) categories. During training, patients will be instructed to contact the PD clinic if one or more of the hydration metrics indicate action required.

Planned research procedures: Our project has 5 research procedures, all of which will collect private, identifiable patient information.

1. *Monitoring for abnormal hydration metrics by PD clinic staff:* PD clinic staff will review the CKD-PD web application daily for outlier alerts. Outliers are determined based on the hydration metric parameters set by the nephrologist at enrollment. See 4.2.a.3 below.

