2. *Clinical intervention for overhydration:* Change in medical treatment in response to OH detected by clinical symptoms or hydration metrics. Interventions may include a change in medications to treat OH such as anti-hypertensives or diuretics, dialysis prescription, dietary sodium/fluid restriction, referral for evaluation in clinic, or hospitalization. This information will be collected in the electronic PD clinic study log at the time of the clinical intervention.
3. *Unscheduled clinic contacts:* When patients in either group make an unscheduled contact with the PD clinic this will be recorded in the PD clinic electronic study log. Unscheduled clinic contact can also occur in the “app” group when PD clinic staff contact a patient in response to abnormal hydration metrics. Unscheduled contacts include any phone call, text, social media, or web app message, and unscheduled visit to the PD clinic or emergency department. The information collected included patient name/MR#, reason for contact, mode of contact, who initiated contact, date and time of day, and action taken. Unscheduled clinical interventions will be recorded at the time of the event.
4. *Scheduled clinic contacts:* Patients in both groups will have regularly scheduled clinic visits, typically bimonthly. Clinical interventions for OH made during this visit will be recorded in the electronic PD clinic study log. A medical record review will also occur at each visit to collect any other hospitalizations, complications, or clinical interventions that may have occurred in the interim.
5. *CKDNET database review:* In order to ensure all events have been captured, we will review the CKDNET database, which has all inpatient and outpatient visits, on a bimonthly basis.

Data collection overview

Data elements for analysis of covariates at enrollment: These will include: age, sex, educational level, cause of CKD, eGFR, co-morbidities (e.g. diabetes, hypertension, albumin level), previous hospitalizations for OH, smoking status, distance from clinic, months on PD, months of CKD-PD usage, and app user type (patient or surrogate). The source will be medical records and patient interview at time of enrollment.

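### The hydration metrics behind the primary count are not planned baseline covariates, and the 25% precision depends on a doubling that no reported rate supports

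*Combined protocol and SAP*

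**What the plan says.** **Eligibility.** The Aim 2 inclusion criteria admit "patients with CKD from any cause on home based peritoneal dialysis", aged 18 or over, with a suitable smartphone and demonstrated ability (patient or surrogate) to use the app. There is no hydration or blood pressure criterion.

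**What produces an event.** Under Clinical interventions, an event is a treatment change made for abnormal hydration metrics or for symptoms of overhydration (OH). A contact without a change in management does not count. Under Monitoring CKD-PD smartphone and web applications, weight, blood pressure and ultrafiltration volume trigger the action-required alerts. A study nephrologist sets each patient's limits "at the time of enrollment after reviewing previous values from their PD logbook".

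**Baseline covariates.** The enrolment list includes "co-morbidities (e.g. diabetes, hypertension, albumin level), previous hospitalizations for OH", together with demographic, renal and app-use items. It names no blood pressure, weight or ultrafiltration value.

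**Adjustment.** Statistical Design and Power adjusts the primary rate difference for important covariates that are imbalanced at baseline.

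**Sample size.** The same section derives 80 per group "using the difference in incidence rates between two Poisson means with 25% precision", from 2.3 interventions per patient-year in 91 Srinagarind patients and an assumed 4.6 with the app, "using a two-sided, large-samples z-test of the Poisson event-rate difference at a significance level of 0.05". It states no power. The doubling is attributed to experience with 42 current users: "In those 42 patients, especially those with unstable fluid and blood pressure control, the app frequently identifies outlier measurements".

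**The concern.** A patient whose readings are often outside the limits at entry can generate many interventions in the year, and a well-controlled patient few. Baseline values of the three metrics are therefore likely to be among the strongest predictors of the primary count. If they are not analysis variables, a chance imbalance in them cannot be seen directly. The precision that adjustment would bring is lost even when the arms are balanced. Baseline status also cannot be reconstructed cleanly once the app has begun to change care.

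The second part concerns the planning figure. The account of the 42 users describes outlier readings and opportunities to intervene, not counted interventions. It gives no rate, denominator or comparator, and it does not say how the users were selected or how many had unstable control. The stated precision is relative to the assumed difference, so it is only as good as the doubling.

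**Working it through.** **1. Covariates.** Setting the sections side by side:

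- Event definition and alert rules: blood pressure, weight against dry weight, ultrafiltration volume, and symptoms.
- Enrolment covariates: none of the three metrics. The nearest items are a hypertension diagnosis and previous OH admissions.
- Adjustment rule: only covariates found imbalanced.
- Data source: the paper logbook, which is usual care, with past values reviewed at enrolment to set alert limits.

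The information exists at enrolment but is not carried into the analysis plan. The gain from adjustment cannot be calculated, because the documents give neither the between-patient variance of the count nor its association with the baseline metrics.

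**2. Reproducing the 80 per group.** Inputs from Statistical Design and Power:

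- control rate r0 = 4 × 52 / 91 = 2.29, stated as 2.3 per patient-year;
- app rate r1 = 4.6, so the difference is 2.3;
- 25% precision, read as a 95% half-width of 0.25 × 2.3 = 0.575;
- z = 1.96, with one year of follow-up per patient.

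n = z² × (r0 + r1) / (0.25 × (r1 − r0))² = 3.8415 × 6.9 / 0.575² = 80.2. This matches the plan. A power calculation for 2.3 against 4.6, n = (1.96 + z_power)² × 6.9 / 2.3², gives 11 per group at 80% power and 14 at 90%. So 80 is a precision figure.

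**3. The same formula at smaller effects.** Half-width = 1.96 × √((2.3 + r1) / 80). Power = Φ(difference / SE − 1.96), where SE = √((2.3 + r1) / 80). Both assume Poisson variance. The rate ratios below 2 are sensitivity values, since the documents give none.

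| Rate ratio | App rate | Difference | Half-width | Half-width / difference | Power | n per group for 25% |
|---|---|---|---|---|---|---|
| 2.0 | 4.6 | 2.3 | 0.576 | 25.0% | >99.9% | 80.2 |
| 1.75 | 4.025 | 1.725 | 0.551 | 31.9% | >99.9% | 131 |
| 1.5 | 3.45 | 1.15 | 0.525 | 45.7% | 99.0% | 268 |

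At 1.5, for example: √(5.75 / 80) = 0.268; 1.96 × 0.268 = 0.525; 0.525 / 1.15 = 45.7%; and 1.15 / 0.268 − 1.96 = 2.33, which gives 99.0%.

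**The case against.** The best defence is that little depends on this. Randomisation within site keeps the comparison unbiased whatever the baseline mix. The absolute half-width is nearly constant, and Poisson power at a rate ratio of 1.5 is still 99%. The covariate list has proxies and is introduced as a list of what will be included, so it need not be exhaustive. The adjustment rule would act on an imbalance in those proxies. Alert limits are individual and can be modified, so no single baseline classification matches exactly what triggers each patient's alerts.

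The points on bias, absolute precision and power stand, so this is not a threat to validity. The point on individual limits also stands, and is a reason to keep any analysis by baseline status exploratory. The proxies are a weaker defence. Hypertension is a diagnosis rather than a measure of control, and the Aim 1 subject description calls it common in this population. Previous OH admission misses patients who were overhydrated but not admitted: in 2016, 39 of 91 Srinagarind patients (43%) were admitted for any cause, while the background section estimates that 50-60% of PD patients are overhydrated.

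A reader might go further in two ways that the documents do not support.

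- *That the doubling comes from unstable users and so describes a different population from a trial open to every PD patient.* The word especially is emphasis within all 42 users, not a restriction, and nothing shows that they differ from future participants. The control rate comes from 91 clinic patients at the site that supplies 100 of the 200 participants. Nor is every PD patient admitted: smartphone access and demonstrated app use are required, which makes participants resemble existing users in those respects.
- *That the effect can be diluted by the background shares of overhydrated or symptomatic patients.* Those shares do not measure unstable control. The calculation would also need equal base rates and no effect at all in stable patients, and neither has a source.

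**Conclusion.** Two things hold. First, the three metrics behind the alerts and the event definition are not on the enrolment covariate list, and the adjustment rule is conditional on observed imbalance, so a likely strong predictor of the primary count is left out of the planned adjustment. Its predictive strength is inferred from the event definition and alert rules; no data on it are given, and the gain is not quantified.

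Second, the doubling is an assumption without a reported intervention rate behind it, and the 25% precision holds only if it is met. Relative precision is about 32% at a rate ratio of 1.75 and 46% at 1.5. These figures assume a control rate of 2.3, 80 patients per group with a full year each, and Poisson variance; greater variation between patients would widen every interval. The practical loss is in relative precision and in how a modest result can be read. Bias is not at issue, and under these assumptions power is not either for ratios of 1.5 and above.

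**What to change.** 1. **Data collection.** Before allocation and in both arms, record baseline blood pressure, weight against dry weight and ultrafiltration volume from the logbook, over a stated look-back period. The existing logbook review is described under app monitoring, so the text should say that recording covers the no-app group too.
2. **Covariate list.** Add the three metrics to the data elements collected at enrolment.
3. **Analysis.** In Statistical Design and Power, define baseline hydration status from these values in advance, identically in both arms. Adjust the primary rate difference for it regardless of observed imbalance. Report the app effect by baseline status as exploratory only.
4. **Sample size text.** State that the doubling is an assumption not backed by a reported intervention rate in the 42 users, and that their selection and stability mix are not described. Add that 25% precision requires the doubling, and give the figures for rate ratios of 1.75 and 1.5.

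The cost is transcription of logbook values at enrolment, some protocol wording, and a stated precision that looks less favourable. Eligibility, sample size, the primary outcome, alert limits and clinical care are unchanged.

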Clinical interventions used: We will record the type of clinical intervention, patient symptom/hydration metric abnormality, whether it was occurred from a scheduled or unscheduled communication, and ordering clinician. This information will be recorded in an electronic study log at time of PD clinic visit, or time of communication to patients.

Outcome measures: Our primary outcome measure will be the incidence of clinical interventions for OH in 1 year from enrollment. Secondary outcome measures include OH-related complications

Drop out/Lost to follow up: The number of patients who drop out, are lost to follow up or died during the study period will be collected. This information will be collected from chart reviews and PD clinic communications and recorded in the electronic clinic study log.

PD clinic/patient communications: We will also collect data about communications between PD clinic staff patients or their surrogates by logging phone calls and messaging app contacts. This information will include who initiated the call, whether or not it resulted in a clinical intervention, the type of clinical issue, and mode of communication. This information will be recorded in the PD clinic electronic study.

Potential risks to participants: This study poses low risk to participants with regard to physical, psychological, social, cultural or legal aspects as both groups receive the same standard of care as currently provided to PD patients at the study site nephrology clinics, including routine clinic appointments, medications, dialysis prescriptions, dietary recommendations, educational and other community support networks, and urgent services e.g. phone contact to PD clinic, unscheduled clinic visits, and emergency care. We have identified some potential specific risks including data breaches, lost or malicious hacking of computers, loss of privacy, concern about change or access to PD care, over or under identification of overhydration, failure to detect life threatening outlier data points in a timely fashion, technology failure, communication failures and errors, and unintended consequences of using a new technology. Strategies to mitigate these risks are discussed below. Alternative strategies available to participants are the option to decline or withdraw from the research at any time.

Informed Consent and Assent

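### The primary identity-link Poisson model leaves its random effect, person-time and site unspecified, and can give non-positive rates and a shrunken difference if continuous covariates enter

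*Combined protocol and SAP*

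**What the plan says.** The primary analysis is given in the Aim 2 section Statistical Design and Power: "A linear mixed model with an identity link and a Poisson distribution will be performed". Its purpose follows: "By this modeling, the incidence rate difference and its 95% confidence interval will be estimated to answer the primary research question". Adjustment is left to what the data show: "Estimations will be adjusted for effects of important covariates that are imbalanced at baseline". No criterion for importance or imbalance is given.

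The candidate covariates, under Data collection overview, mix continuous and categorical items: "age, sex, educational level, cause of CKD, eGFR, co-morbidities (e.g. diabetes, hypertension, albumin level), previous hospitalizations for OH", and the list goes on to include distance from clinic and months on PD.

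The outcome is one count of OH interventions per patient over one year. The Randomization section allocates patients within each of three sites. Under Drop out/Lost to follow up the plan will collect "The number of patients who drop out, are lost to follow up or died during the study period", but it does not say how these patients enter the model. The analysis text also names no random effect, does not mention site, and has no provision for overdispersion or for a fit that fails.

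The planning rate is "4 times/week in 91 patients or a mean intervention rate of 2.3 times/patient-year", and it is "based on current practice of patients contacting the PD clinic staff with symptoms or concerns of OH outside of scheduled appointments".

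**The concern.** An identity link makes each fitted rate a sum of covariate terms, and nothing keeps that sum above zero. A Poisson mean must be positive, so a continuous covariate can carry some patients into an impossible range.

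The model's name adds doubt. With one count per patient and three sites, a reader cannot tell whether the mixed term is a patient effect, a site effect or neither.

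Person-time scales an expected count. Under an identity link it must multiply every term, and the plan does not say that it will.

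If the adjusted fit fails or gives impossible rates, the plan has no next step. The analyst would then have to drop covariates or change the model with outcomes in view. The headline estimate and its interval could depend on that choice.

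**Working it through.** **Inputs from the plan.** Rates of 2.3 (control) and 4.6 (app) per patient-year, so a difference of 2.3; 80 evaluable per group; 25% precision; 10% dropout; one year of follow-up. Covariate strength and between-patient variance are not given. They are assumed below and shown over a range.

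**1. The plan's own figure.** 4 × 52 / 91 = 2.29, stated as 2.3. Read as a half-width of 25% of the difference, 0.25 × 2.3 = 0.575, the size is n = 1.96² × (2.3 + 4.6) / 0.575² = 80.2 per group. This reproduces 80. The half-width of 0.575 is a useful yardstick for the errors below.

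**2. Non-positive fitted rates.** Trials were simulated with 80 per group at rates 2.3 and 4.6, covariates acting multiplicatively, and patient-level (gamma) variance from 0 to 1. The identity-link Poisson likelihood was maximised. The table gives the share of trials with at least one fitted rate at or below zero.

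| Continuous covariates | Rate ratio 1.28 per SD | Rate ratio 1.10 per SD |
|---|---|---|
| One | about 5-12% | 0% |
| Two | about 20-33% | 0-2% |
| Four | about 60-69% | 2-14% |

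Independent repeats agree to within a few percentage points. With no covariates, or binary ones only, the share is about 0%. With both rates doubled (4.6 and 9.2) and a rate ratio of 1.28, it falls to 0-4%, 10-20% and 29-48%.

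**3. Size of the adjusted difference.** In simulations with multiplicative covariate effects and a true difference of 2.3, the adjusted identity-link estimate averages about 2.2 with one continuous covariate and 1.8 with four. The reason is that the Poisson likelihood gives more weight to patients with low fitted rates, in whom a multiplicative app effect is a smaller absolute difference. The shortfalls of 0.1 and 0.5 are 17% and 87% of 0.575.

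**4. Raw counts without person-time.** Suppose that those who leave do so, on average, halfway through the year.
- 10% dropout in both arms: mean follow-up 0.95, so 0.95 × 2.3 = 2.19 (simulated 2.19).
- 20% app and 5% control: 4.6 × 0.90 − 2.3 × 0.975 = 1.90 (simulated 1.91).

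Against 2.30, the simulated values are short by 0.11 and 0.39, or 19% and 68% of 0.575. Multiplying each term by follow-up time, so that the mean count is t × (b0 + b1 × arm), recovered 2.29 to 2.32 in every dropout pattern tried.

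**5. Extra-Poisson variation.** With patient-level variance v, the variance of a count is μ + vμ². At v = 0.5:
- control: 2.3 + 0.5 × 2.3² = 4.945
- app: 4.6 + 0.5 × 4.6² = 15.18
- sum 20.125, against 6.9 under Poisson, a ratio of 2.92

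The true standard error is √2.92 = 1.71 times the model-based one. A nominal 95% interval then reaches only 1.96 / 1.71 = 1.15 true standard errors, which is about 75% coverage. Robust errors restore about 95%.

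**The case against.** The identity link is a legitimate and direct route to the rate difference that the plan wants. Since both distribution and link are stated, the intended model is reasonably clear despite its loose name. That stands.

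A reader might infer that the model will often give negative rates. The documents do not support this, for three reasons.
- Only imbalanced covariates enter. Take five independent continuous covariates with imbalance judged at p < 0.05: the chance that two or more qualify is 1 − 0.95⁵ − 5 × 0.05 × 0.95⁴ = 2%. With an absolute standardised difference above 0.2 as the criterion it is 28%, and 0.8% for four or more. Both criteria are assumptions, because the plan gives none. The four-covariate row therefore describes an unlikely model under such rules.
- The rate of 2.3 counts unscheduled contacts only, while the outcome also counts routine interventions. True rates are probably higher, which lowers the shares.
- Covariate strength is assumed, and weak effects give few or no such fits.

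Nor do these percentages measure failure to converge. A maximum can exist with a non-positive fitted rate for a patient with no events, and on average no more than about 2% of patients were affected.

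A reader might also infer that person-time cannot be used under an identity link. That is wrong: the plan never proposes an additive offset, and multiplying every term by time works. The gap is that the plan is silent.

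Finally, choosing covariates by imbalance would remain a problem under a log link, so changing the link alone is not enough.

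**Conclusion.** The concern holds as one of under-specification with measurable consequences. The plan fixes neither the random effect nor the handling of person-time, does not mention the randomization stratum, and has no fallback. Unadjusted, or with binary covariates, the identity-link model behaves well.

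The risk of impossible rates, and the pull of the adjusted difference towards 1.8, depend on how many continuous covariates enter and how strong they are. The imbalance rule leaves the number unknown until the data are in. The person-time error depends on dropout, and is worst when the arms differ. The loss of coverage depends on between-patient variation, for which the documents give no figure.

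None of this shows that the primary analysis will fail. It shows that the headline estimate and interval could move by a material part of the planned precision through choices not yet made.

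**What to change.** **Preferred.** Fit a Poisson regression with robust standard errors (or a negative binomial regression), log link and offset log(person-years observed). Include arm, site as a fixed effect, and a short list of covariates named before outcomes are seen. Obtain the incidence rate difference and its 95% CI by averaging the predicted rates under each arm over all randomized patients, and report the rate ratio beside it.

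**Alternative.** Keep the identity link, with every term multiplied by person-time, robust errors, site and named covariates. Name the log-link model above as the fallback if any fitted rate is non-positive or the fit fails.

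Either version should state whether there is a random effect and, if so, for what.

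**Cost.** Some wording in the analysis section and one post-estimation step, with a delta-method or bootstrap interval for the difference. The rate difference stays the headline estimate, and the sample size of 80 per group is unaffected.
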